11.2. Data Capture, Review, and Validation

Data entered in the EDC system will be verified against the source data by NBI (or designee). Any discrepancies will be corrected on-line by authorized site personnel. Automated (computergenerated) logic checks will run in order to identify items such as inconsistent study dates. In addition, manual review/checks may be conducted by NBI on the data. Any inconsistencies/errors/omissions identified will be sent to the site (via an electronic query) for the necessary corrections to be made to the eCRF. Once entered and saved in an eCRF, data immediately become part of the study database and are available to NBI.

11.3. Coding Dictionaries

AEs and medical history will be coded using the chosen version of the Medical Dictionary for Regulatory Activities (MedDRA). Prior and concomitant medications will be coded using the chosen version of the World Health Organization Drug Dictionary (WHODrug).

12. STATISTICAL AND ANALYTICAL PLAN

Descriptive statistical methods will be used to summarize the data from this study. The term "descriptive statistics" refers to the number of subjects (n), mean, median, SD, SEM, minimum, and maximum for continuous variables, and refers to the number of subjects (or events) and percentage for categorical variables. Confidence intervals may be presented for selected variables as well.

Detailed descriptions of the data summaries that will be presented for this study will be provided in the expanded Statistical Analysis Plan (SAP). The SAP will be developed prior to locking the study database.

12.1. Analysis Sets

Data summaries for this study will be based on the safety analysis set, which will include all subjects who receive a dose of study drug. Additional analysis sets may be specified in the SAP.

12.2. Sample Size

The sample size for this study is based on practical clinical considerations with no formal statistical power calculations.

12.3. Handling of Missing Data

All available study data will be included in relevant summaries and data displays, including any available data for subjects with incomplete or missing data.

12.4. Disposition of Subjects

A summary of subject disposition will be prepared that displays the number of subjects who were enrolled, received study drug, and completed the study. The number of subjects who did not complete the study will be displayed both overall and by reason for discontinuation.

12.5. Demographics and Baseline Characteristics

Age, height, weight, BMI, gender, race, ethnic group, and screening 17-OHP levels will be summarized with descriptive statistics.

12.6. Pharmacokinetic Data

Descriptive statistics and graphical displays will be presented for NBI-74788 and metabolites plasma concentrations by scheduled sampling time. For these summaries, values that are below the limit of quantitation (BLQ) will be set equal to zero.

Individual subject plasma concentration vs. time plots will also be presented.

The following plasma PK parameters will be calculated for NBI-74788 and metabolites using noncompartmental methods and summarized by dose cohort using descriptive statistics:

- Area under the plasma concentration versus time curve from 0 to 12 hours (AUC₀₋₁₂)
- C_{max}
- Time to reach C_{max} (t_{max}).

Additional PK parameters for Day 14 to 15 only:

- Average plasma concentration at steady state (C_{avg})
- Percent fluctuation at steady state (%fluctuation)
- Accumulation ratio at steady state
- t½
- Apparent terminal rate constant (λz)
- Apparent mean residence time (MRT)

• Apparent systemic clearance after oral administration (CL/F) (NBI-74788 only).

12.7. Pharmacodynamic Data

Morning 17-OHP (serum; ng/dL) from the 8- and 12-hour postdose samples (collected at 0300 and 0700 hours).

17-OHP at all other times, androstenedione (serum; ng/dL), testosterone (serum; ng/dL), cortisol (serum; μ g/dL), and adrenocorticotropic hormone (ACTH; plasma; pg/mL). Summaries of PD measures will include both observed values and changes from timepoint-matched PD baseline values.

12.8. Safety Data

TEAEs, categorized by system organ class (SOC) and/or preferred term as defined by MedDRA, will be summarized. A TEAE is defined as any AE that occurs after the first dose of study drug. Any AE that occurred before the first dose of study drug will be considered a pretreatment AE. The TEAE tables will include the number and percentage of unique subjects experiencing each event.

Clinical laboratory data, vital sign measurements, ECG data, and other safety data will be summarized by timepoint (as appropriate) with descriptive statistics.

12.9. Interim Analysis

An interim analysis is not planned for this study.

13. REGULATORY AND ETHICAL ISSUES

13.1. General Legal References

The study will be carried out according to the provision of the US CFR, the US Food and Drug Administration (FDA), Canada Food and Drugs Act and Regulations, Health Canada, and the ICH Guidelines for GCP. All clinical work conducted under this protocol is subject to GCP rules. This includes an inspection by NBI or its representative, health authority, or IRB representatives at any time. The investigator must agree to the inspection of study-related records by health authority representatives and/or NBI or its designee.

13.2. Institutional Review Board

The final approved protocol and the consent/assent documents will be reviewed by the IRB for the clinical site. The committee's decision concerning conduct of the study will be sent in writing to the investigator and a copy will be forwarded to NBI. The investigator must agree to make any required progress reports to the IRB, as well as reports of SAEs, life threatening problems, or death.

13.3. Protocol Adherence and Amendments

The protocol must be read thoroughly, and the instructions must be followed exactly. Any changes in the protocol will require a formal amendment. Such amendments will be agreed upon and approved in writing by the investigator and NBI. The IRB will be notified of all amendments to the protocol. Amendments to the protocol will not be implemented until written IRB approval has been received.

13.4. Required Documents

The investigator must provide NBI or its representatives with the following documents before the enrollment of any subject (originals should be kept by the investigator in the investigator's regulatory document binder):

- Signed copy of the approved protocol signature page.
- Investigator's Brochure acknowledgement page.
- Completed and signed statement of investigator (Form FDA 1572) and/or Clinical Trial Site Information Form, as applicable.
- Curriculum vitae and current medical license of the investigator and subinvestigators.
- Financial disclosure information as required.
- Letter of approval from the IRB for the protocol and consent documents.
- Copy of the IRB approved written ICF to be used.
- Laboratory documents (certifications/accreditations, normal ranges) if not provided by a central laboratory.

13.5. Informed Consent

Parent(s) or legal guardian(s) will provide informed consent with signed (or verbal, if applicable) and witnessed study subject assent before the performance of any study-related procedures.

Each subject's chart will include the signed ICF with signed and witnessed study subject assent (or confirmation of verbal assent) for study participation. When the study treatment is completed and the eCRF has been monitored, the ICF and signed and witnessed study subject assent will be kept in the investigator's central study file. Regulatory authorities may check the existence of the signed ICF and the signed and witnessed study subject assent in this central study folder.

13.6. Study Monitoring

Throughout the course of the study, the study monitor will make frequent contacts with the investigator. This will include emails, telephone calls, and on-site visits. During the on-site visits, the eCRFs will be reviewed for completeness and adherence to the protocol. As part of the data audit, source documents will be made available for review by the study monitor. The study monitor will also perform drug accountability checks and may periodically request review of the investigator study file to ensure completeness of documentation in all respects of clinical study conduct.

Upon completion of the study, the study monitor will arrange for a final review of the study files after which the files should be secured for the appropriate time period. The investigator or appointed delegate will receive the study monitor during these on-site visits, will cooperate in providing the documents for inspection, and respond to inquiries. In addition, the investigator will permit inspection of the study files by authorized representatives of the regulatory agencies.

13.7. Quality Assurance

The study will be conducted in accordance with NBI's standard operating procedures designed to ensure that all procedures are in compliance with GCP, FDA Guidelines, Health Canada Guidelines, and according to national law. Quality assurance audits may be conducted at the discretion of NBI.

13.8. Record Retention

Federal regulations require that records of drug disposition, eCRFs, and all reports of this investigation shall be retained by the investigator for a minimum of 2 years after notification by NBI that the regulatory authorities have been notified of the study's termination, or 2 years after approval of the marketing application. If the investigator is unable to retain the study documents for the required amount of time, NBI must be informed of the individual who will be assuming this responsibility.

13.9. Confidentiality

NBI and the clinical site affirm and uphold the principle of the subject's right to protection against invasion of privacy. Throughout this study, all data will be identified only by an identification number.

All information concerning this study and which was not previously published is considered confidential information. This confidential information shall remain the sole property of NBI; it shall not be disclosed to others without written consent of NBI; and shall not be used except in the performance of this study.

The information compiled during the conduct of this clinical study is also considered confidential and may be disclosed and/or used only by NBI as deemed necessary. To allow the use of the information derived from this clinical study and to ensure compliance with current federal regulations, the investigator is obliged to furnish NBI with the complete test results and all data compiled in this study.

14. STUDY COMMENCEMENT AND DISCONTINUATION

Upon satisfactory receipt of all required regulatory documents, NBI (or designee) will arrange that all study material be delivered to the study center. Subject entry should not begin until after the required regulatory documents are confirmed as received, and the Investigator Meeting/Initiation Meeting has occurred. All personnel expected to be involved in the conduct of the study will undergo orientation to include review of study protocol, instructions for eCRF

Neurocrine Biosciences, Inc., Study No. NBI-74788-CAH2008 Clinical Protocol Final Version

completion, AE reporting, and overall responsibilities including those for drug accountability and study file maintenance.

If the study is discontinued, all subjects should undergo a complete follow up examination. Any clinically relevant finding, including laboratory values of potential clinical concern, and adverse experiences will be followed until they resolve or return to a clinically acceptable level.

1. LIST OF ABBREVIATIONS

Table 1: List of Abbreviations

17-OHP	17-hydroxyprogesterone
ACTH	Adrenocorticotropic hormone
AE	Adverse event
ALT	Alanine aminotransferase
ALP	Alkaline phosphatase
AST	Aspartate aminotransferase
AUC	Area under the plasma concentration versus time curve
AUC ₀₋₁₂	AUC from 0 to 12 hours
BMI	Body mass index
BPRS-C	Brief Psychiatric Rating Scale for Children
BSA	Body surface area
САН	Congenital adrenal hyperplasia
C_{avg}	Average plasma concentration at steady state
CL/F	Apparent systemic clearance after oral administration
C _{max}	Maximum plasma concentration
CSR	Clinical study report
C-SSRS	Columbia-Suicide Severity Rating Scale, Children's Version
CV	Coefficient of variation
ECG	Electrocardiogram
eCRF	Electronic case report form
ET	Early termination
GGT	Gamma-glutamyl transferase
ICH	International Council for Harmonisation of Technical Requirements for Pharmaceuticals for Human Use
IPD	Important protocol deviation
λz	Apparent terminal rate constant
MedDRA	Medical Dictionary for Regulatory Activities
MRT	Mean residence time
NBI	Neurocrine Biosciences, Inc.
PD	Pharmacodynamic(s)

PK	Pharmacokinetic(s)
PT	Preferred term
QTcF	Corrected QT interval using Fridericia's formula
SAE	Serious adverse event
SAP	Statistical analysis plan
SD	Standard deviation
SE	Standard error
SOC	System organ class
TEAE	Treatment-emergent adverse event
t _{1/2}	Terminal half life
t _{max}	Time to maximum plasma concentration
ULN	Upper limit of normal
WHO	World Health Organization

2. INTRODUCTION

The purpose of this statistical analysis plan (SAP) is to describe the planned analyses and data displays that will be prepared to summarize the data from the Phase 2 study described in Neurocrine Biosciences, Inc. (NBI) Protocol NBI-74788-CAH2008.

This SAP was developed in accordance with ICH (International Council for Harmonisation of Technical Requirements for Pharmaceuticals for Human Use) E9 guidance. All decisions regarding the final analysis, as defined in this SAP document, will be made prior to database lock. Changes made to the planned analyses after finalization of this SAP and database lock will be described in the clinical study report (CSR). Further information related to study design and methodology can be found in the protocol.

3. STUDY OBJECTIVES

3.1. Study Objectives

The objectives of the study are as follows:

- To assess the safety and tolerability of crinecerfont (NBI-74788) in pediatric subjects 14 to 17 years of age with congenital adrenal hyperplasia (CAH).
- To evaluate the effect of repeated doses of crinecerfont on endogenous levels of pharmacodynamic (PD) biomarkers in pediatric subjects with CAH.
- To evaluate the pharmacokinetics (PK) of crinecerfont and metabolites in pediatric subjects with CAH.

4. STUDY DESIGN

4.1. Summary of Study Design

This is a Phase 2, open-label, multiple-dose study to assess the safety, tolerability, PK, and PD of crinecerfont in approximately 12 pediatric female and male subjects (14 to 17 years of age) with a documented medical diagnosis of classic 21-hydroxylase deficiency CAH. Crinecerfont 50 mg bid will be administered for 14 consecutive days with breakfast and evening meals beginning on the evening of Day 1.

[figure not shown]
Eligible subjects who have a screening 17-OHP level ≥800 ng/dL will be admitted to the study center on Day -7 for 1 night and have baseline serial PD samples collected over a 24-hour period beginning that evening. Baseline serial PD samples will be collected at approximately 1845, 2000, 2300, 0100, 0300, 0700, 1000, 1500, and 1900 hours.

The subjects' usual morning dose of steroidal treatments will be administered after the 1000 hours PD sample is collected on Day -6. Subjects will be discharged on Day -6 after the last PD sample is collected.

Subjects will be admitted to the study center on Days 1 and 14 (first and last day of dosing). The first dose of study drug, crinecerfont 50 mg, will be administered at approximately 1900 hours with subjects' evening meal on Day 1. Study drug will be administered at the study center on Days 2 and 14 with subjects' breakfast and evening meals, respectively. The subjects' usual morning dose of concurrent steroidal treatments, study drug dosing, and breakfast (snacks will be allowed prior to breakfast) will be delayed until after the 15-hour postdose PD samples are collected (ie, at approximately 1000 hours) on Day 2. The subjects' usual morning dose of concurrent steroidal treatments will be administered after the 15-hour postdose PD samples are collected (ie, at approximately 1000 hours) on Day 15. Study drug will be self-administered at home under parent/guardian supervision at approximately 0700 hours (with breakfast) and 1900 hours (with evening meal) on Days 3 to 13.

The study design schematic is shown in Figure 1.

Figure 1: Study Design Schematic

bid=twice daily; ET=early termination; PD=pharmacodynamic; NBI-74788=crinecerfont.

4.2. Sample Size Considerations

The sample size for this study is based on practical clinical considerations with no formal statistical power calculations.

4.3. Clinical Assessments

Pharmacodynamic assessments include:

- Morning 17-OHP (serum; ng/dL) from the 12- and 15-hour postdose samples (collected at 0700 and 1000 hours).
- 17-OHP at all other times, androstenedione (serum; ng/dL), testosterone (serum; ng/dL), cortisol (serum; μg/dL), and adrenocorticotropic hormone (ACTH; plasma; pg/mL).

Pharmacokinetic assessments include:

The following plasma PK parameters will be calculated for crinecerfont and metabolites for the Day 1 to 2 and the Day 14 to 15 sampling intervals:

- Area under the plasma concentration versus time curve from 0 to 12 hours (AUC $_{0-12}$).
- Observed maximum plasma concentration (C_{max}).
- Time to C_{max} (t_{max}).

Additional PK parameters for Days 14 to 15 only:

- Average plasma concentration at steady state (C_{avg}).
- Percent fluctuation at steady state (%fluctuation).
- Accumulation ratio at steady state.
- Apparent terminal half-life ($t\frac{1}{2}$).
- Apparent terminal rate constant (λz) .
- Apparent mean residence time (MRT).
- Apparent systemic clearance after oral administration (CL/F) (crinecerfont only).

Safety assessments include:

- Adverse events (AEs).
- Clinical laboratory tests (clinical chemistry, hematology, and urinalysis).
- Vital signs.
- Physical examinations (including musculoskeletal exam).
- 12-lead electrocardiograms (ECGs).
- Columbia-Suicide Severity Rating Scale (C-SSRS), Children's Version

• Brief Psychiatric Rating Scale for Children (BPRS-C).

See Table 2 of the study protocol for a complete schedule of assessments.

5. PLANNED ANALYSES

5.1. Interim Analyses

No interim analysis is planned for this study.

5.2. Final Analyses

Final analyses, as specified in the protocol and in this SAP, will be performed after the study database has been locked.

6. GENERAL CONSIDERATIONS FOR DATA ANALYSES AND HANDLING

All analyses described in this plan are considered *a priori* analyses in that they have been defined prior to locking the study database. Analyses defined subsequent to locking the database will be considered *post hoc* analyses and will be applied as exploratory methodology. Any *post hoc* analyses will be clearly identified in the CSR.

6.1. General Statistical Procedures

Descriptive statistical methods will be used to summarize the data from this study. The term "descriptive statistics" refers to the number of subjects, mean, median, standard deviation (SD) or standard error (SE), minimum, and maximum for continuous and ordinal categorical variables; and refers to the number and percentage of subjects (or events) for categorical variables. Additional descriptive statistics, such as the coefficient of variation (CV), will be presented for selected PK data.

Unless otherwise noted, data will be summarized by a single dose group (crinecerfont 50 mg bid). For the purposes of PD data summaries, serial sampling that starts at the 15 minutes preevening dose on Study Day 1 and continues until the 24 hours post-evening dose on Study Day 2 will be referred to as "Day 1"; serial sampling that starts at the 15 minutes pre-evening dose on Study Day 14 and continues until the 24 hours post-evening dose on Study Day 15 will be referred to as "Day 14" in the data summaries.

Summary statistics will be displayed using the following decimal precision rules: the minimum and maximum will have the same number of decimal places as the data; the mean, median, SD, and SE will have one more decimal place than the data being summarized. Percentages will be displayed using one decimal place; percentages for 0 counts will be omitted. These rules may be modified if warranted, based on practical considerations.

6.2. Analysis Sets

6.2.1. Definition of Analysis Sets

6.2.1.1. Safety Analysis Set

The safety analysis set will include all subjects who take at least one dose of study drug and have any postbaseline safety data. The safety analysis set will be used for all summaries of safety data (e.g., AEs, clinical laboratory data) and pharmacokinetic data.

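### The SAP narrows the protocol's safety set by also requiring postbaseline safety data and applies it to PK, so a dosed subject with no such data would leave the safety and PK summaries (rare; minor)

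*SAP*

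**What the plan says.** Protocol 12.1 bases the data summaries on "the safety analysis set, which will include all subjects who receive a dose of study drug". It adds: "Additional analysis sets may be specified in the SAP". This allows further sets and does not mention narrowing the safety set. Protocol 12.3 brings all available data into the relevant summaries, "including any available data for subjects with incomplete or missing data".

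SAP 6.2.1.1 reads: "The safety analysis set will include all subjects who take at least one dose of study drug and have any postbaseline safety data". It says that this set "will be used for all summaries of safety data (e.g., AEs, clinical laboratory data) and pharmacokinetic data". SAP Table 2 confirms the scope: plasma concentrations, PK parameters, adverse events, laboratory data, vital signs, weight, ECG, C-SSRS and BPRS-C all use the safety set. The SAP defines a separate pharmacodynamic set (6.2.1.2) but no PK set.

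SAP 6.2.2 tabulates exclusions from each set by reason. SAP 6.2.3 bases disposition and analysis-set status on all enrolled subjects.

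**The concern.** Safety and tolerability is the first listed objective in both documents, and the natural denominator for it is everyone exposed. The SAP makes membership depend on what happens after the first dose. Such a condition can remove exposed subjects and can never add one.

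The condition is also loosely worded. The SAP does not say whether adverse event monitoring that records no event counts as safety data, so two programmers could classify the same subject differently.

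The same condition decides who enters the PK summaries, although having a safety record has no bearing on whether a concentration is valid.

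**Working it through.** The documents give no figure to reproduce: the sample size of about 12 has no power basis, and no dropout rate is stated. The check compares the definitions, then asks who could be removed, then sizes the effect.

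**1. Definitions.**

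| | Protocol 12.1 | SAP 6.2.1.1 |
|---|---|---|
| Received a dose | required | required |
| Has postbaseline safety data | not required | required |

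The SAP set is therefore the protocol set or a part of it.

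**2. Who could be removed.** SAP 6.3.1 takes baseline as the last value before dosing, so anything recorded after the first dose is postbaseline. Protocol 8.7.3.1 gives this sequence:

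| Time after first dose | Scheduled |
|---|---|
| Evening of Day 1 | Adverse event monitoring |
| 1, 4 and 6 h | PK and PD samples |
| 8 to 10 h | Vital signs (first measured safety data with a stated postdose time) |
| Day 2 | Physical examination and ECG |
| About 24 h | Discharge, after the 24-hour procedures |

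Protocol 8.10.1 also calls for early termination assessments after every premature discontinuation. Removal therefore requires a subject to leave within hours of the first dose, before the 8 to 10 h vital signs, with no adverse event recorded and no termination visit. A subject lost after the Day 2 discharge would normally stay in the set.

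**3. Effect on adverse event percentages.** A recorded postdose adverse event is itself postbaseline safety data, so the numerator k cannot change. Only the denominator moves, from k/12 to k/11, a factor of 12/11 = 1.09. The removal of one or two subjects is an assumption.

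| Denominator | k = 1 | k = 3 | Upper bound for k = 0 |
|---|---|---|---|
| 12 (all dosed) | 8.3% | 25.0% | 22.1% |
| 11 (one removed) | 9.1% | 27.3% | 23.8% |
| 10 (two removed) | 10.0% | 30.0% | 25.9% |

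The last column is the one-sided 95% bound 1 − 0.05^(1/n). For n = 12 it is 1 − 0.05^(1/12) = 0.221. The visible SAP plans no such bound for adverse events, so the column only illustrates scale.

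Protocol 7.3 allows replacement of subjects who discontinue for reasons other than TEAEs. If the removed subject were replaced, 13 would have been exposed and 12 shown: 3/12 = 25.0% against 3/13 = 23.1%. The table total of 12 would then not reveal the removal, although the analysis-set summary would.

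**4. Effect on PK.** Three postdose samples fall before the 8 to 10 h vital signs. A subject who leaves in that gap with no safety record could lose up to three concentrations, so the Day 1 summaries at 1, 4 and 6 h would each rest on 11 values instead of 12. AUC0-12 would be little affected, because samples ending at 6 h do not span its interval. PD samples are drawn at the same times, and SAP 6.2.1.2 does not require safety data. The same subject, if he or she had a PD baseline value, would be in the PD set but outside the safety and PK summaries.

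**The case against.** The strongest case on the other side is that the condition asks for any postbaseline safety data, so under this schedule it may never exclude anyone. If monitoring without an event counts as data, the clause is close to empty. If an exclusion did occur, it would be reported with its reason. The study is single-arm and descriptive, with no power calculation. The proposed change has a cost of its own: a subject never observed after dosing would count as having no event, which lowers the percentages. All of this stands, and it limits the point to a minor one. It does not remove the contradiction with Protocol 12.1 or give a reason to tie PK inclusion to safety data.

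A reader might infer more than the documents support:

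- That any dosed subject lost early drops out of the tables. Only a subject with no postbaseline safety data at all does.
- That harm could be hidden. A recorded postdose adverse event keeps the subject in the set, so an exclusion leaves a percentage at zero or raises it.
- That safety results are dropped against Protocol 12.3. A removed subject has no postbaseline safety result to drop, so only the PK part conflicts with that section.
- That the change was made without explanation. SAP Section 12, where departures from the protocol's planned analysis belong, shows no text in the public version, so nothing can be concluded from its silence.

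The protection is nevertheless not complete. Subjects may leave at any time and loss to follow-up is a listed withdrawal reason (Protocol 8.10.1), while Protocol 8.10.2 says only that withdrawn subjects will be asked to have the termination assessments.

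**Conclusion.** The point holds as a minor inconsistency. SAP 6.2.1.1 narrows a set that Protocol 12.1 defines as every dosed subject, and it carries that narrowing into PK. The expected number removed is assumed to be 0 or 1, because the documents give no dropout rate. If one of 12 were removed, an event in three subjects would read 27.3% instead of 25.0%, and up to three valid concentrations could be left out. If none were removed, every table would be the same under either definition. The reason to act is that the safety denominator should not depend on follow-up and that the correction is nearly free. The likely numerical effect is small.

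**What to change.** In SAP 6.2.1.1, delete the requirement for postbaseline safety data, so that the safety set is every subject who takes at least one dose, as in Protocol 12.1. Summaries of measured values should continue to show the number of subjects with data at each visit.

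For PK, base the summaries on dosed subjects with at least one evaluable postdose concentration, keep the SAP 10.1 exclusions for significant deviations, and update SAP Table 2 to match.

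The cost is one deleted clause, one short definition and a table edit, with no new data. The downside is that a dosed subject with no postbaseline observation would stay in the adverse event denominator as having no recorded event. A footnote giving the number of such subjects makes this visible.
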